13.5 Clinical Safety Laboratory Investigations

Not applicable.

13.6 Concomitant Medication

The frequencies and percentages of concomitant medications will be tabulated overall and by vaccine group. Medications (generic drug name) will be coded using the WHODRUG dictionary.

14. INTERIM ANALYSIS

14.1 Interim Analysis

As the circulation of influenza viruses is seasonal and the event rates of influenza are difficult to predict, this study is group sequentially, with a case count-driven interim analysis if decided by the Sponsor. The goal of the Interim Analyses is, first, to minimize the risk of not being able to take a significant test decision after the end of the study, and second, to be able to stop the study for early evidence of efficacy.

The number of laboratory-confirmed influenza cases will be reviewed on a regular basis. If decided by the Sponsor and after observing at least 50% of planned events meeting the co-primary endpoint, an interim analysis for efficacy may be performed for evaluation by a DMC.

- If the number of RT-PCR confirmed influenza cases is less or equal to 190 overall, no interim analysis for efficacy may be done and the study will be extended because the probability to make a conclusion for efficacy is too low.
- If the number of RT-PCR confirmed influenza cases is greater or equal to 191 but less than 381 unblinded interim analyses for efficacy may be performed for evaluation by the DMC (see below for description and DMC charter). To maintain the overall alpha, $\alpha = 2.5\%$ (1-sided), for the hypotheses testing for the primary objectives, an error-spending-function will be used. The benefit of using an error-spending-function is that no maximum number of analysis stages and the timing of the analyses need to be pre-specified, what in practice means that the duration of the study in terms of number of seasons can be left open. In this case α -boundaries, forming the adjusted probabilities for the type I error, are calculated using error-spending function and if the p-values for both primary objectives are lower than the respective α -boundary the trial stops early (i.e., without reaching the targeted number of cases of 381) for efficacy. Otherwise, the trial continues enrollment. Decisions to stop or continue the trial will be made on the basis of discussions between the DMC and Senior Management.
- If the number of RT-PCR confirmed influenza cases is greater or equal to 381 (targeted number of cases to be able to evaluate the co-primary objective) and subjects have been enrolled over at least three seasons the study will be unblinded and the final analysis will be performed by the sponsor. If the trial proceeds to the final analysis (upon reaching 381 cases) the boundaries for acceptance or rejection are identical to the assumed type 1 and type 2 errors for the overall design, and the trial stops to either reject or not reject the null hypothesis of the primary objective.

That is, the primary objective, i.e. VE against RT-PCR or culture confirmed influenza A and or B will be assess the one-sided 0.025 alpha level.

In case the DMC states that the observed data provides already the full information level needed for the final test decision, then the final analysis can be done on full alpha level of (2.5 % 1-sided) and no further enrollment is needed. If, however, the decision of the group-sequential test is to continue the study then it is on the DMC to determine the number of subjects needed to be enrolled. The DMC should not be influenced by the individual results of the vaccine groups observed at an interim analysis stage when planning further subjects' accrual or the times of future analysis. Only the overall number of cases is allowed to be used for further planning. The following formula for determination of sample sizes for further enrollment may be used:

$$N_{\text{total}} = (C_{\text{planned}} - C_{\text{observed}}) / [(ER_{\text{QIVc}} + ER_{\text{comp}})/2],$$

where N_{total} denotes the total number of subjects needed for further enrollment, C_{planned} is the overall number of cases needed for the test, i.e. 381 cases, C_{observed} are the at that stage observed number of cases overall, and ER are the respective event rates assumed for each group, i.e., 8.0% for non-influenza comparator group and 4.0% for QIVc.

For the analysis of for efficacy, an error-spending function will be applied to provide statistical stopping rules for efficacy (α -boundaries) for the first interim analysis and second interim analysis, if necessary, based on the information accumulated until that specific interim stage, i.e. based on the accumulated variance of the parameter of interest.

These boundaries will be calculated on a p-value see:

<https://support.sas.com/documentation/onlinedoc/stat/131/seqdesign.pdf>

At each interim stage, α -boundaries, forming the adjusted probabilities for the type 1 error, are calculated using error-spending function and if the p-value for the test of primary objective is lower than the respective α -boundary the trial stops for efficacy at this stage.

In other words the trial stops early for efficacy if data collected at this stage allows to demonstrate both primary and co-primary efficacy objectives (reject null-hypothesis). Further guided by efficacy estimates of QIVc described in secondary efficacy objective 4 (prevention of PCR confirmed influenza antigenic matched to the strains selected for the seasonal vaccine). Otherwise, the trial continues to the next stage and more subjects will be enrolled.

The cumulative O'Brien-Fleming type error-spending-function ([Lan and DeMets, 1983](#), option ERRFUNCOBF in SAS[®] PROC SEQDESIGN) will be used for both α - and β -boundaries; the error-spending function is defined as:

$$E(t; a) = \begin{cases} 1 & \text{if } t \geq 1 \\ \frac{1}{a} 2 (1 - \Phi(\frac{z(1-a/2)}{\sqrt{t}})) & \text{if } 0 < t < 1 \\ 0 & \text{otherwise} \end{cases}$$

where a equals α for α spending function and β for beta spending function, and where t is the information fraction.

If the trial proceeds to the final analysis, the boundary for rejection of null hypothesis is identical to the type 1 error (that is as the 0.025 one-sided alpha level) with power specified for the overall design, and the trial stops to either reject or not reject the null hypothesis of the primary objective.

Additional interim analyses may be requested at a future date (by the DMC), particularly if the first interim analysis is conducted soon after 191 cases of influenza have been reported. In this case, the DMC may request that a second interim analysis be conducted to allow for greater accuracy to determine if the trial should stop or continue.

Any modifications of a trial design (i.e. introducing additional interim analysis stage) and calculations of number of subjects to be additionally enrolled will be based on the assumptions as defined in the protocol Section 8.6, and will not be influenced by the results of an interim analysis.

Table 14.1-1 shows the needed total number of cases at each stage of the two-stage design together with boundaries for early stopping efficacy, calculated on p-value scale using the cumulative error spending function. With ½ information collected at the stage of interim analysis (that is, with exactly 191 confirmed ILIs) the trial would stop early for efficacy if the p-value is lower than 0.00282. Otherwise the trial will be continued and more subjects will be enrolled. The actual boundaries used for decision making would depend on number of confirmed ILIs occurring and reported for Interim Analysis.

Table 14.1-1: Example of a Two Stages Group-Sequential Design

	Stage 1 First Interim	Stage 2 Final
Number of Events	191	382
Alpha Boundary on p-value scale (equivalent to Type 1 error, 1-sided), early stopping for efficacy	0.00282	0.02518

The stopping rules are statistically determined and should be complemented by clinical and strategic stopping rules that allow the DMC to make a decision on a broader picture of the data which includes safety endpoints and the other endpoints of the study being for example secondary efficacy objective 4. Another interim look at the data with appropriate adjustment of type 1 error might be recommended before reaching the targeted 381 cases.

For the interim analyses, if needed a restricted unblinding will be done, i.e. only independent DMC members and unblinded individuals responsible for the analyses will receive access to the randomization codes and unblinded data for the purpose of preparing the interim analyses (further information on handling of the blinding for the interim analyses can be found in the DMC charter [and protocol section 3.3](#)). The results of the interim analyses will be used only for DMC purposes and will not be reported in a CSR.

The comparison of the test statistic with its boundary values will be performed by using the SAS[®] SEQTEST procedure. The boundary information tables calculated by PROC SEQDESIGN at an analysis stage are structured for input to the SEQTEST procedure. At each subsequent stage, the boundary values are derived by using the test information tables created by the SEQTEST procedure at the previous stage. These test information tables are also structured for input to the SEQTEST procedure. PROC SEQTEST can also be used to compute parameter estimates, confidence limits, and p-values after the trial stops.

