Seqirus UK Ltd	V130_12	Cell-Based Quadrivalent Subunit Influenza Virus Vaccine (QIVc) Meningococcal (Groups A, C, Y, W-135) Conjugate Vaccine (Men ACWY)

If the number of influenza cases in the cohort ≥ 3 years to < 18 years of age is greater or equal to 191 but less than 381 an interim analysis for efficacy and futility with an appropriate adjustment of the type I error will be conducted by a DMC, to decide if study objectives have been reached or the study may be extended to an additional season. The need for further interim analyses and further extensions will be assessed by the DMC. If it is determined that the study objectives have been reached, enrolment will be halted.
 
If the number of influenza cases in the cohort ≥ 3 years to < 18 years of age is greater or equal to 381 (targeted number of cases to be able to evaluate the co-primary objective) the study will be unblinded and the final analysis will be performed.
 
A final clinical study report will present all efficacy, immunogenicity and safety data collected from the treatment period through to the end of follow-up period (180 days following the last vaccination dose, or until the end of influenza season, whichever is longer).
		

Number of Subjects planned:
 
Assuming an approximate 10% drop out rate, minimally 7,692 male and female subjects ≥ 2 years and < 18 years of age are planned to be enrolled. Subjects will be randomized in a 1:1 ratio to receive QIVc (n=3,846) or non-influenza comparator vaccine (n=3,846). Approximate numbers of subjects planned for enrollment in the age groups are presented below.
		

Name of Sponsor: Seqirus UK Ltd	Protocol number: V130_12	Generic name of study vaccine(s): Cell-Based Quadrivalent Subunit Influenza Virus Vaccine (QIVc) Meningococcal (Groups A, C, Y, W-135) Conjugate Vaccine (Men ACWY)
---	------------------------------------	--

[Table 1. Approximate Number of Subjects Planned for Enrollment](#)

Age cohort	≥2 to <9 years of age		≥9 to <18 years of age	Total
	“not previously vaccinated” Subjects	“Previously Vaccinated” Subjects		
QIVc	1,022 to 1,430	614 to 1,022	1,803	3,846
Men ACWY	1,022 to 1,430	614 to 1,022	1,803	3,846
Total	2,044 to 2,860	1,228 to 2,044	3,606	7,692

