2.1.2 Primary and Co-Primary Endpoint

The primary and co-primary efficacy endpoint is the time from the last study vaccination to the onset of the first occurrence confirmed influenza by either RT-PCR-confirmed or culture-confirmed, due to any influenza Type A or B strain regardless of antigenic match to the strains selected for the seasonal vaccine, occurring > 14 days after the last vaccination and until the end of the influenza season.

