5. SAMPLE SIZE AND POWER CONSIDERATIONS

This study is planned using a group sequential design, with one or more interim analyses for efficacy using O'Brien-Fleming efficacy bounds. The statistical test performed will depend only on the number of confirmed ILI cases (events), so the sample size estimate is only for operational reasons (an estimate of number of subjects needed to assess the endpoint).

Primary Efficacy Objective ≥ 2 years to < 18 years of age

Estimated sample size to arrive at 298 events, is 4,814 evaluable subjects (or 2,407 evaluable subjects per treatment group), assuming attack rate in non-influenza comparator vaccine subjects of 8%, vaccine efficacy of 45%, and the risk of infection contained entirely within period covered by follow-up. Accounting for early dropout and uncertainty about the assumed parameters, 5,349 subjects are planned to be enrolled to demonstrate that the lower limit of the two-sided 95% CI for the VE is greater than 20% for the primary endpoint assessment, with approximately 90% power.

Co-primary Efficacy Objective ≥ 3 years to < 18 years of age

Assuming a true vaccine efficacy of 50% it was calculated that approximately 381 observed confirmed ILI cases would be needed to demonstrate that the lower limit of the two-sided 95% CI for the VE is greater than 30% with approximately 90% power.

The statistical test performed will depend only on number of confirmed ILI cases (events), so sample size estimate is only for operational reasons. Estimated sample size to arrive at 381 events, is 6,350 evaluable subjects (or 3,175 evaluable subjects per treatment group), assuming attack rate in non-influenza comparator vaccine subjects of 8%, assumed vaccine efficacy of 50%, VE is greater than 30%, and the risk of infection contained entirely within period covered by follow-up. Accounting for early dropout and uncertainty about the assumed parameters, 7,056 subjects are planned to be enrolled to demonstrate that the lower limit of the two-sided 95% CI for the VE is greater than 30%.

Table 5-1 summarizes the power calculations assumptions and the number of events required to meet primary and co-primary endpoint.

Table 5-1 Power calculation for Primary and Co-Primary Endpoints

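### The 190/191/381 case triggers are not tied to the co-primary events for which 381 was sized; on an all-ages reading the final analysis could start with about 350 co-primary events

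*SAP*

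**What the plan says.** **The target.** SAP section 5 and Protocol 8.5 derive 381 for the co-primary objective, age 3 to <18 years: "Assuming a true vaccine efficacy of 50% it was calculated that approximately 381 observed confirmed ILI cases would be needed" to show that the lower limit of "the VE is greater than 30% with approximately 90% power". SAP 2.1.2 defines the endpoint as "confirmed influenza by either RT-PCR-confirmed or culture-confirmed", with onset more than 14 days after last vaccination and by the end of the season.

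**The triggers in the SAP.** Section 14.1 has three bullets, at 190, 191 and 381. Each counts RT-PCR confirmed cases; none names an age group, culture or the >14-day window. The lowest reads "If the number of RT-PCR confirmed influenza cases is less or equal to 190 overall" and the highest "If the number of RT-PCR confirmed influenza cases is greater or equal to 381". The word *overall* is not in the 191 and 381 bullets, but it returns in the re-enrolment formula, where observed cases overall are subtracted from 381. The 381 bullet also links that number to the co-primary objective and requires enrolment over at least three seasons.

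**The triggers in the protocol.** The synopsis study design text has "If the number of influenza cases in the cohort ≥ 3 years to < 18 years of age is greater or equal to 381", and its 191 trigger has the same limit. Its 190 trigger does not, nor do the synopsis interim section, Protocol 3.1 or Protocol 8.6. Section 8.6 itself adds *overall* to 190 and has the same formula. The protocol's definition of an influenza case is RT-PCR or culture.

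**The concern.** The 381 count decides when the trial is unblinded for its final analysis, and the co-primary test is what sets the trial size. Cases in 2-year-olds inform the primary objective but not the co-primary. If they count toward 381, the co-primary analysis is run on fewer events than planned. Culture-only cases do the reverse: they enter the analysis but not the SAP's count.

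The primary objective is not at risk from this, since it needs 298 endpoint events at all ages. What is at stake is some co-primary power, and a decision rule that two careful readers could apply differently.

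**Working it through.** **Inputs.** Margin VE 30% (hazard ratio 0.70); true VE 50% (0.50); attack rates 8% and 4%; 1:1 allocation; 10% dropout; final boundary described in SAP 14.1 as "that is as the 0.025 one-sided alpha level"; 7,692 enrolled in all, 7,056 of them aged 3 to <18; at most 635 aged 2. (7,692 − 7,056 is 636; the difference is immaterial here.)

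**1. Reproduce 381.**
- Schoenfeld: D = 4(1.960 + 1.282)² / [ln(0.50/0.70)]² = 371.2, so 372. Freedman's formula gives 379. The plan's 381 is within 3% of both.
- Subjects: 381 / 0.06 = 6,350 evaluable; 6,350 / 0.9 = 7,056 enrolled. Both match.
- Power at D events = Φ(0.3365 × √(D/4) − 1.960). At 381: 0.907. One O'Brien-Fleming type look at half information gives 0.906.

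**2. All-ages reading, cap filled, equal attack rates and dropout by age.**
- Share aged 2: 635 / 7,692 = 8.26%.
- Cases outside the co-primary: 381 × 0.0826 = 31.5, which leaves 349.5, about 350.
- Power: 0.882, a loss of 2.5 points. If the variance uses the expected 1:2 split of events between arms, power goes from 0.872 to 0.843; the level is lower but the loss is similar.

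**3. Range.** The documents give neither the actual share *s* of 2-year-olds nor their attack-rate ratio *r* to older children, so both are assumed. Share of cases f = sr / (sr + 1 − s); shortfall = 381f.

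| s | r | Shortfall | Power |
|---|---|---|---|
| 0 | any | 0 | 90.7% |
| 3% | 1 | 11 | 89.9% |
| 5% | 1 | 19 | 89.3% |
| 8.26% | 1 | 31 | 88.2% |
| 8.26% | 2 | 58 | 85.6% |

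**4. Case definition.** RT-PCR positives are a subset of RT-PCR-or-culture positives. Within one age range and time window, 381 RT-PCR cases mean at least 381 endpoint cases, so this mismatch works against the shortfall. No rate of culture-only cases is given.

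**5. Time window.** Protocol 3.5 has swabs taken from Day 1. Read literally, the SAP bullets could admit cases before the >14-day window, which would add to the shortfall. No rate is given for these either.

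**6. Interim.** 191 all-age cases at the cap would hold 191 × 0.9174 = 175 co-primary cases, or 46% of 381. SAP 14.1 separately requires at least 50% of planned co-primary events.

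**7. Count needed on an all-ages basis.** 381 / 0.9174 = 415. Planned enrolment is expected to yield 7,692 × 0.9 × 0.06 = 415.

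**The case against.** Several stronger conclusions are tempting, and the documents do not support them.

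- *That the SAP departs from a clear protocol rule.* Only the synopsis study design text gives the age range. Protocol 3.1 and 8.6 have none, and 8.6 also says *overall* at 190. The inconsistency lies within the protocol as well.
- *That the SAP sets 381 at all ages.* It does not say so. Its 381 bullet points to the co-primary objective, and *overall* in the re-enrolment text may mean both vaccine groups pooled, since the same paragraph tells the DMC not to use results by group. The all-ages reading is an inference, though a reasonable one: 190 and 191 are adjacent branches of one rule and must use one count.
- *That RT-PCR-only counting makes the shortfall worse.* It offsets it (step 4).
- *That the interim could be run at 46% information.* The separate 50% condition, repeated in SAP sections 3, 5 and 15, bars it.
- *That alpha spending would be wrong.* SAP 14.1 says boundaries depend on the number of confirmed ILIs, but also that they rest on accumulated variance, and Protocol 8.4.2.2.4 takes information from the fitted model. Misstated spending is not shown.
- *That early unblinding is certain.* No minimum number of 2-year-olds is set, the three-season condition may carry the count past 381, and full enrolment is expected to give about 415 all-age cases.

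All of this stands, and it limits the size of the problem. None of it supplies the missing definition.

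**Conclusion.** The point holds as an inconsistency in both documents over which events are counted at 190, 191 and 381. The RT-PCR-only wording in the SAP is a plain mismatch with the endpoint. The missing age range matters only if 381 is applied to all ages. In that case, with the cap on 2-year-olds filled, equal attack rates and a stop at exactly 381, the co-primary would be tested on about 350 events with power of 88.2% instead of 90.7%. Across the assumed shares of 3% to 8.26% and attack-rate ratios of 1 to 2, the shortfall is 11 to 58 events and power is 89.9% to 85.6%; with no 2-year-olds nothing is lost. These figures take no account of culture-only cases or of cases before the >14-day window, for which the documents give no rates. The effect is modest and conditional. It concerns power and the clarity of a decision rule, not type I error.

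**What to change.** Define the 190, 191 and 381 counts once, as first-occurrence RT-PCR- or culture-confirmed influenza with onset more than 14 days after last vaccination and by the end of the season, in subjects aged 3 to <18 years. Put that definition in SAP 14.1, in Protocol 3.1 and 8.6, and in the study design and interim analysis parts of the synopsis. Apply it to planned and observed cases in the re-enrolment formula, say whether *overall* there means pooled over vaccine groups, and note that the formula then returns children of that age. Use the same count for the co-primary information fraction.

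The cost is wording. The final analysis may come slightly later, at about 415 all-age cases if the cap is filled, which the planned enrolment of 7,692 is already expected to yield.

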11. EFFICACY ANALYSIS

11.1 Primary Efficacy Objectives Analysis

Efficacy will be evaluated in all subjects in relation to cases occurring >14 days after last vaccination and until the end of study or the end of the influenza season, whichever is longer, using the following null (H_0) and alternative (H_1) hypotheses:

$$H_0: 1 - HR = VE \leq 0.2 \quad \text{versus} \quad H_1: 1 - HR = VE > 0.2,$$

where HR is a hazard ratio of QIVc versus non-influenza comparator and VE is vaccine efficacy. The primary objective will be achieved if the lower limit of the two-sided confidence interval of VE estimate, with at least 95% coverage in a multiple sequential hypothesis testing, exceeds 0.2 in subjects ≥ 2 years to <18 years of age.

The co-primary objective will be achieved if the lower limit of the two-sided confidence interval of VE estimate, with at least 95% coverage in a multiple sequential hypothesis testing, exceeds 0.3 in subjects ≥ 3 years to <18 years of age.

The co-primary objective will only be demonstrated in case of successful demonstration of the primary efficacy objective (i.e. in hierarchical testing procedure, only after demonstration of absolute vaccine efficacy of QIVc in subjects ≥ 2 years to <18 years of age).

In case an interim analysis will be performed the 95% CI will be adjusted accordingly. If an interim analysis is performed and the trial doesn't stop, then all the subsequent analysis will be tested at a reduced alpha level, i.e. what's left from the interim analysis. The confidence interval will be higher than 95% instead of 95% for the final analysis.

(Co-)Primary vaccine efficacy analyses will be based on the Efficacy FAS, and repeated on the Efficacy PPS.

For each of the age groups (≥ 2 to <18 and ≥ 3 to <18 years), the HR² and the related 95% CI of HR, for onset of first RT-PCR or culture confirmed influenza will be estimated by a proportional hazards regression model with treatment effect as a fixed effect and stratifying covariates as random effect:

$h_i(t|X) = h_0(t) \exp(\beta^T X + b^T Z)$, with t denoting time to the influenza, β is the effect of treatment group indicated by X , b is random effect (assumed as a multivariable random gaussian variable with zero mean and diagonal covariance matrix), Z is random effect covariate (reflecting randomization strata, see [Section 8.1](#) for further discussion of the covariates utilized).

² Formula: $VE=1-HR$

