Subjects that did not experience ILI during observation period and subjects that dropped out from the study during observational period will be censored (right-censoring). The estimate of the hazard ratio, the respective estimate for absolute VE and the pertaining two-sided CIs will be calculated based on this model. If the study continues over several seasons, estimates will be also adjusted for the factor season (s). In case of one or two (interim) analyses, confidence levels at each stage will be adjusted, as discussed in section 14.1, to provide 95% overall coverage.

For each of the age groups (≥ 2 to <18 and ≥ 3 to <18 years), estimates for hazard ratio in Cox Proportional hazard (PH) model will be calculated using Maximum Likelihood (ML) method. In case of problems with convergence (algorithm does not converge or converges to infinite estimates) penalized ML approach will be used (Heinze and Schemper).

Vaccine efficacy $VE = 1 - HR$, that is, $1 - \exp(\hat{\beta})$

with $\hat{\beta}$ with $100(1 - \alpha)$ percent confidence interval as:

$[1 - \exp(+Z(s.e.(\hat{\beta}))); 1 - \exp(\hat{\beta} - Z(s.e.(\hat{\beta})))]$. Z is the $100(1 - \alpha)$ percent point of the standard normal distribution, and s.e. denotes the standard error of β

Subjects that did not experience ILI during observation period and subjects that dropped out from the study during observational period will be censored (right-censoring).

The hazard ratio is the predicted ratio of cases of Influenza A and or B disease in subjects receiving QIVc and non-influenza vaccine comparator within each of the strata of interest. The term β_g is the estimate of treatment effect (or regression coefficient) between QIVc and non-influenza vaccine comparator within each of the stratum.

The estimate of the hazard ratio, the respective estimate for absolute VE and pertaining two-sided 95% CIs will be calculated based on this model. If the study continues over several seasons, estimates will be also adjusted for the factor season (s). Factor country might be added to the model if appropriate. In case of more than one interim analysis confidence level for the estimates at the final stage will be adjusted.

Primary analysis will take into account only first ILI episode for a subject.

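### SAP 14.1 tests the final analysis at the full one-sided 0.025 (0.02518 in Table 14.1-1) even after an efficacy interim, so the co-primary test exceeds the promised 2.5%

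*SAP*

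**What the plan says.** SAP 14.1 sets the overall error at one-sided 2.5%, to be held by an error-spending function over an optional efficacy interim at 191 to 380 cases. The trial stops early only "if the p-values for both primary objectives are lower than the respective" boundary. For the final analysis the section states the level three times, each time as the whole alpha:

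- at 381 cases, "the boundaries for acceptance or rejection are identical to the assumed type 1 and type 2 errors for the overall design";
- the primary objective "will be assess the one-sided 0.025 alpha level";
- if the trial reaches the final analysis, "the boundary for rejection of null hypothesis is identical to the type 1 error (that is as the 0.025 one-sided alpha level".

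Table 14.1-1 gives an example: 0.00282 at 191 events and 0.02518 at 382 events, one-sided. The text introducing it says these are "calculated on p-value scale using the cumulative error spending function".

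SAP 11.1 gives the contrary rule. After an interim, "all the subsequent analysis will be tested at a reduced alpha level", with a final confidence interval wider than 95%, and "confidence levels at each stage will be adjusted, as discussed in section 14.1, to provide 95% overall coverage". So 11.1 sends the reader to 14.1 for the adjustment, and 14.1 does not make it.

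Two further texts bear on the level. SAP 8.3 prescribes a power-family spending function with rho = 2, whereas 14.1 prescribes a Lan-DeMets O'Brien-Fleming type. SAP 14.1 gives no futility stop, yet its formula still carries the words "for beta spending function, and where". Protocol 8.6 does describe a futility stop and applies the full-error final boundary to either or both primary objectives.

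**The concern.** If a trial can claim success at an interim and, failing that, is tested again at the full 0.025, the two chances of a false claim together exceed 0.025. A final level above 0.025, such as 0.02518, is valid only when a binding futility stop removes some null trials before the final test. The SAP has no such stop: a trial that misses the interim boundary continues.

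The excess is small, but this is the pass/fail threshold for a confirmatory claim (VE above 30% in subjects aged 3 to under 18 years). After one interim, the SAP supports four different final levels:

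- 0.0218: SAP 11.1 with the 8.3 function;
- 0.0245: SAP 11.1 with the 14.1 function;
- 0.025: SAP 14.1 text;
- 0.02518: SAP 14.1 table.

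Nothing in the SAP or protocol says which governs, so the choice could be left until results are known. A final interval at the full level would also miss the 95% overall coverage promised in SAP 11.1.

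**Working it through.** **Inputs.** Overall one-sided alpha 0.025; interim at 191 of 382 events, so t = 0.5; boundaries 0.00282 and 0.02518 (all SAP 14.1). Co-primary null VE 30%, assumed VE 50%, 381 events (SAP 5). Both spending functions as printed in SAP 8.3 and 14.1.

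**Method.** The interim and final statistics are bivariate normal with correlation √0.5. The error is P(Z1 > c1 or Z2 > c2) under the null.

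**1. Where the table comes from.** The 14.1 function at a = 0.025, t = 0.5 gives 2[1 − Φ(2.2414/√0.5)] = 2[1 − Φ(3.170)] = 0.001525, not 0.00282. Adding binding beta spending with the same function gives 0.00153/0.02526, still not the table. A classical O'Brien-Fleming design with efficacy bounds only gives 0.00258/0.0240. The printed pair is reproduced by a classical O'Brien-Fleming design with *binding* futility, alpha 0.025 and beta 0.10: 0.00282/0.02518, with a futility p-value of about 0.331. So 0.02518 is not an arithmetic slip; it belongs to a design that the SAP does not describe.

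**2. Error of the rules as written, no futility stop.** For the table pair, c1 = 2.768 and c2 = 1.957, and P(Z1 > 2.768 or Z2 > 1.957) = 0.02627.

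| Interim rule | Final level | Co-primary error |
|---|---|---|
| 0.00282 | 0.02518 | 0.0263 |
| 0.00282 | 0.025 | 0.0261 |
| 14.1 function, one look (0.00153) | 0.025 | 0.0255 |
| 14.1 function, looks at t = 0.5 and 0.75 (0.00153, 0.00916) | 0.025 | 0.0277 |
| 8.3 function, one look (0.00625) | 0.025 | 0.0280 |
| 8.3 function, looks at t = 0.5 and 0.75 (0.00625, 0.01094) | 0.025 | 0.0305 |

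The two-look timing is an assumption; SAP 14.1 allows a second interim without fixing when.

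**3. Does the hierarchy remove the excess?** The co-primary at its null was simulated with the primary as gate and the rule that both must cross to stop (4 million trials per scenario). It was assumed that 92% to 100% of events fall in subjects aged 3 or more, with VE of 0 to 30% in the 2-year-olds. After a 0.00282 interim, the error was 0.0260 to 0.0261 with a 0.025 final and 0.0261 to 0.0263 with 0.02518. The gate does not remove it.

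**4. The primary objective.** At true VE 20% in both age groups, the co-primary crosses 0.00282 at half information with probability only 0.00011, so almost no primary alpha is used early. Simulated primary error under the same rules is 0.0250 to 0.0252 (correlation between the two tests assumed to be √(7,056/7,692) = 0.958).

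**5. Protocol 8.6 with futility.** If the futility stop is obeyed as binding, the table pair gives 0.0250, and 0.00282 with a 0.025 final gives 0.0248: no inflation. If the stop is overridden, the table pair returns to 0.0263.

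**6. Final levels that hold 0.025 after one interim, efficacy only.** Drift for power: ln(0.7/0.5) × √(381/4) = 0.3365 × 9.760 = 3.284.

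| Interim / final | Final CI | Chance of crossing co-primary interim bound at VE 50% | Overall co-primary power, 381 cases |
|---|---|---|---|
| 0.00153 / 0.0245 (14.1 function) | 95.1% | 26% | 90.6% |
| 0.00625 / 0.0218 (8.3 function) | 95.6% | 43% | 90.0% |
| 0.00282 / 0.0239 (interim value kept) | 95.2% | 33% | 90.5% |
| 0.00282 / 0.02518 (table as printed) | 95.0% | 33% | 90.9% |

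With two interims at t = 0.5 and 0.75, the final levels would be 0.0220 (14.1 function) and 0.0184 (8.3 function).

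**The case against.** The best defence is that the SAP already contains the right rule. Section 11.1 requires a reduced level, 14.1 promises error spending, and its closing paragraph has SEQTEST derive each later boundary from the stage before. Table 14.1-1 is labelled an example, and the text says that actual boundaries will depend on the case count. On this reading the defect is contradictory wording. Part of that stands: an analyst who followed 11.1 and ran SEQTEST on an efficacy-only design would control the error. But the full-alpha sentences are not examples, they are the only ones in 14.1 that state the final level, and 11.1 defers to 14.1.

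Second, the SAP sentences name the primary objective, for which there is essentially no excess. True of the wording, but the table is built on the co-primary event count, and Protocol 8.6 applies the same boundary to both objectives.

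Third, the interim is optional, and 0.025 is correct without one. This stands and limits the finding; but the table shows the near-full level after an interim.

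Fourth, Protocol 8.6 has a futility stop under which the table pair holds 0.025. Also true, if the stop is binding. The SAP describes its interim as efficacy-only and lets the DMC weigh other evidence, so that cannot be relied on.

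Last, the larger figures (0.0277 to 0.0305) combine a spending function with an unadjusted final level. That combination is what 14.1 prescribes if read literally, but the size with one O'Brien-Fleming-type look is only 0.05 to 0.13 percentage points.

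**Conclusion.** The concern holds: the final level in SAP 14.1 is wrong as written whenever an unblinded efficacy interim has been taken. The co-primary error is then 0.0255 to 0.0263 with one O'Brien-Fleming-type look, 0.0277 with two looks under the 14.1 function, and 0.0280 (one look) or 0.0305 (two) under the 8.3 function, against a promised 0.025. The primary objective is not materially affected. These figures assume looks at half (and three-quarters) information and no futility stop that must be obeyed. The excess is modest. It should still be corrected before any unblinding, because the documents leave the co-primary threshold undetermined between 0.0218 and 0.02518 and the correction costs almost nothing.

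**What to change.** 1. Name one spending function, reconciling SAP 8.3 (rho = 2) with SAP 14.1 (O'Brien-Fleming type), and say that it applies to both hypotheses. Reconcile the leftover beta-spending wording in SAP 14.1 with the futility stop in Protocol 8.6, and state that any futility bound is non-binding for alpha.
2. In SAP 14.1, replace the full-alpha sentences with: *The final boundary is the nominal level remaining from the error-spending function given the looks actually taken; 0.025 applies only if no unblinded efficacy interim took place.* Align the matching sentence in Protocol 8.6.
3. Recompute Table 14.1-1 without futility: 0.00153/0.0245 (14.1 function), 0.00625/0.0218 (8.3 function), or 0.00282/0.0239 if the printed interim value is kept.

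**Cost.** SAP wording, one table and one protocol sentence. The final threshold becomes stricter under every option. The interim threshold becomes stricter under the 14.1 function and looser under the 8.3 function, which moves the chance of crossing the co-primary interim bound from 33% to 26% or 43%. Co-primary power falls by 0.3 to 0.9 points from 90.9%. No extra subjects or cases are needed.
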